Prior research indicates that college students are at high risk for engaging in unintentional and intentional tanning behaviors that dramatically increase their UVR exposure and that they use inadequate sun protection strategies when they are outdoors.^{6,7} However, few studies have examined novel strategies to improve college students' use of sun protection and decrease their intentional tanning behaviors.^{8,9} Prior studies have shown that traditional risk communication strategies do not effectively change college students' health behaviors.^{10,11} It is possible that college students require more novel forms of risk information in order to motivate behavior change, and that these new forms of risk information should be grounded in established theoretical models. In the current study, we will test several theoretically-driven risk communication strategies that aim to improve college students' engagement in skin cancer prevention behaviors, including sun protection behaviors (sunscreen, protective clothing, shade, peak UVR hours avoidance) and tanning behaviors (indoor, outdoor, unintentional).

Based on prior literature,¹² we anticipate low levels of distress regarding *MCIR* feedback. In the current study, we will test several theoretically-driven risk communication strategies that aim to improve college students' engagement in skin cancer prevention behaviors, including sun protection behaviors (sunscreen, protective clothing, shade, peak UVR hours avoidance) and tanning behaviors (indoor, outdoor, unintentional).

Purpose and Objectives

The purpose of this study is to test the feasibility of providing young people with skin cancer prevention education and/or personalized feedback on their risk for skin cancer using novel methods of communicating this risk. In addition, we will examine the effects that the education and risk feedback have on individuals' reported sun protection and tanning behaviors.

Study Population

Age of Participants: 18+

Sample Size:

At Utah: 300

All Centers: 300

Inclusion Criteria:

Individual is enrolled in courses at the University of Utah

And

Individual reports having had at least 1 sunburn in past year

And/or

Individual reports having intentionally indoor or outdoor tanned at least 1 time in the past year

And/or

Individual reports using sunscreen plus 1 or more of the following behaviors never/rarely/sometimes in the past month: 1) Protective clothing items, 2) Shade when outdoors

Exclusion Criteria:

Individual does not read/speak English

Individual reports a personal history of skin cancer

Design

Randomized Trial

Study Procedures

Recruitment/Participant Identification Process:

1) Participants will be recruited through courses at the University of Utah (e.g., through Departments of Communication, Biology, Psychology) in which professors have agreed to offer extra credit in exchange for participation in this study. Professors will be contacted prior to recruitment to determine their willingness to offer extra credit. Information about the study may be made available to potential participants in these courses via in person contact, email, canvas, phone or text.

2) Information will be made available in common areas on campus via flyers (e.g., in the student Union, through campus newspapers, email listservs) including study information and the study team's contact information for potential participants to get in touch if they want to participate. Potential participants will have the option to text the study phone number to be

screened, or complete an online screening form. Study staff may contact participants who screen to be eligible via phone, text, or email.

3) Information about this study may be available on the Huntsman Cancer Institute website and via social media postings (see advertisements attached). Patients who self-refer in response to these advertisements will receive a follow-up from the study team.

Informed Consent:

Description of location(s) where consent will be obtained:

Consent will be obtained from the participant in-person at the University of Utah during visit 1.

Description of the consent process(es), including the timing of consent:

1. Participants will be provided all of the required information about the study via the consent document. 2. We will give participants this information in a language they understand (English). We will use language that is simplified and appropriate for potential participants to understand. Participants that do not speak/read or write in English will be excluded from the study. 3. Participants will be given an opportunity to ask questions before they consent and to ensure that the individual has had enough time to review the consent form to before they sign the consent. The study staff will review the consent form with potential participants and be available to potential participants to ask any questions they may have. 4. Participants will be given time to review the consent and consider being in the study. If the participant wants to take more time to consider whether they want to participate in the study, study staff will schedule another time to complete the consent and visit 1 procedures with them. 5. We will use clear and easy to understand language in the consent document and will not include exculpatory language. 6. Consent will be documented by obtaining a signature from the participant, and study staff will keep the signed document in the research record. 7. Participants will receive a copy of their signed consent documents via email, mail, fax, or in person.

Procedures:

Arm 1: Skin Cancer Education Only

Screening: Participants will have the option to complete an online or text based screening form. Study staff may contact participants who screen to be eligible via phone, text, or email. Study staff will screen potential participants who do not complete the screening form on their own for eligibility. Participants will be contacted by phone, text, or email (starting with the method they indicated would be best to reach them) to schedule their first study visit.

Enrollment

Visit 1: All participants who consent to participate will be asked to participate in up to 3 study visits approximately 4 weeks apart. At visit 1, all participants will be asked to complete informed consent procedures and a baseline questionnaire via computer (e.g., using

Qualtrics) or paper. Participants will be randomized to receive education only, or varying combinations of the intervention components.

Visit 2: At visit 2 participants will receive education on the importance of skin cancer prevention behaviors (e.g., sunscreen, protective clothing) and avoiding tanning and sunburns. All education will be delivered at this visit on a computer screen and additionally given to participants as a handout they can take home to review. When participants view the information on the computer screen, eye tracking will be used to assess participant response. Prior to viewing results, eye tracking equipment set up at the computer station will be calibrated. We will then put up their results on the screen and the imotion system will then track their pupillary movement, facial expression, and galvanic skin response (physiological arousal). Participants will be allowed as much time as they would like to review their results. Following this, participants will complete a post assessment. Participants will receive paper copies of all of the relevant information to take home with them.

Visit 3: Visit 3 may be conducted remotely. At visit 3, participants will complete a follow-up assessment.

Follow-up interview: A random sample of the participant population will be contacted to participate in a follow-up interview with study staff to answer questions about their experience participating in the RISE-UP study.

Arm 2: Skin Cancer Education + UV Photo

Screening: Participants will have the option to complete an online or text based screening form. Study staff may contact participants who screen to be eligible via phone, text, or email. Study staff will screen potential participants who do not complete the screening form on their own for eligibility. Participants will be contacted by phone, text, or email (starting with the method they indicated would be best to reach them) to schedule their first study visit.

Enrollment

Visit 1: All participants who consent to participate will be asked to participate in up to 3 study visits approximately 4 weeks apart. At visit 1, all participants will be asked to complete informed consent procedures and a baseline questionnaire via computer (e.g., using Qualtrics) or paper. Participants will be randomized to receive education only, or varying combinations of the intervention components. Participants randomized to the education + UV photo arm will have their UV light photo taken of their face to show UV damage in the skin that is invisible to the naked eye. Photos will be taken with the VISIA Facial Complexion Analysis System, which captures high resolution imagery at the far spectrum of UVA or long wave UV.

Visit 2: At visit 2 participants will receive education on the importance of skin cancer prevention behaviors (e.g., sunscreen, protective clothing) and avoiding tanning and sunburns. Participants will be provided with their personalized risk feedback based on their personalized photo showing their skin's existing UVR damage from UVR exposure. All information will be delivered at this visit on a computer screen and additionally given to participants as a handout they can take home to review. When participants view their results on the computer screen,

eye tracking will be used to assess participant response. Prior to viewing results, eye tracking equipment set up at the computer station will be calibrated. We will then put up their results on the screen and the imotion system will then track their pupillary movement, facial expression, and galvanic skin response (physiological arousal). Participants will be allowed as much time as they would like to review their results. Following this, participants will complete a post assessment. The imagery resulting will be kept on file in a password protected computer. Participants will receive paper copies of all of the relevant information to take home with them.

Visit 3: Visit 3 may be conducted remotely. At visit 3, participants will complete a follow-up assessment.

Follow-up interview: A random sample of the participant population will be contacted to participate in a follow-up interview with study staff to answer questions about their experience participating in the RISE-UP study.

Arm 3: Skin Cancer Education + MC1R Testing

Screening: Participants will have the option to complete an online or text based screening form. Study staff may contact participants who screen to be eligible via phone, text, or email. Study staff will screen potential participants who do not complete the screening form on their own for eligibility. Participants will be contacted by phone, text, or email (starting with the method they indicated would be best to reach them) to schedule their first study visit.

Enrollment

Visit 1: All participants who consent to participate will be asked to participate in up to 3 study visits approximately 4 weeks apart. At visit 1, all participants will be asked to complete informed consent procedures and a baseline questionnaire via computer (e.g., using Qualtrics) or paper. Participants will be randomized to receive education only, or varying combinations of the intervention components. Participants randomized to the education + MC1R testing arm will be asked to provide a saliva sample. Saliva will be collected by study staff using a system for the collection, stabilization and transportation of DNA from saliva (e.g., Oragene DNA collection kits). Participants will be genotyped for SNPs in MC1R that have been associated with melanoma risk. Genotyping will be done through U of U core facilities

Visit 2: At visit 2 participants will receive education on the importance of skin cancer prevention behaviors (e.g., sunscreen, protective clothing) and avoiding tanning and sunburns. Participants will be provided with their personalized risk feedback based on a summary of their MC1R genetic testing results. All information will be delivered at this visit on a computer screen and additionally given to participants as a handout they can take home to review. When participants view their results on the computer screen, eye tracking will be used to assess participant response. Prior to viewing results, eye tracking equipment set up at the computer station will be calibrated. We will then put up their results on the screen and the imotion system will then track their pupillary movement, facial expression, and galvanic skin response (physiological arousal). Participants will be allowed as much time as they would like

to review their results. Following this, participants will complete a post assessment. Participants will receive paper copies of all of the relevant information to take home with them.

Visit 3: Visit 3 may be conducted remotely. At visit 3, participants will complete a follow-up assessment. Participants who have clinical questions about melanoma or concerns about their family history will be referred to speak with a genetic counselor or be referred to HCI's Family Cancer Assessment Clinic (FCAC) for further information and information on CLIA testing.

Follow-up interview: A random sample of the participant population will be contacted to participate in a follow-up interview with study staff to answer questions about their experience participating in the RISE-UP study.

Arm 4: Skin Cancer Education + UV Photo + MC1R Testing

Screening: Participants will have the option to complete an online or text based screening form. Study staff may contact participants who screen to be eligible via phone, text, or email. Study staff will screen potential participants who do not complete the screening form on their own for eligibility. Participants will be contacted by phone, text, or email (starting with the method they indicated would be best to reach them) to schedule their first study visit.

Enrollment

Visit 1: All participants who consent to participate will be asked to participate in up to 3 study visits approximately 4 weeks apart. At visit 1, all participants will be asked to complete informed consent procedures and a baseline questionnaire via computer (e.g., using Qualtrics) or paper. Participants will be randomized to receive education only, or varying combinations of the intervention components. Participants randomized to the education + UV photo + MC1R testing arm will have a UV light photo taken of their face to show UV damage in the skin that is invisible to the naked eye and will be asked to provide a saliva sample. Photos will be taken with the VISIA Facial Complexion Analysis System, which captures high resolution imagery at the far spectrum of UVA or long wave UV. Saliva will be collected by study staff using a system for the collection, stabilization and transportation of DNA from saliva (e.g., Oragene DNA collection kits). Participants will be genotyped for SNPs in MC1R that have been associated with melanoma risk. Genotyping will be done through U of U core facilities

Visit 2: At visit 2 participants will receive education on the importance of skin cancer prevention behaviors (e.g., sunscreen, protective clothing) and avoiding tanning and sunburns. Participants will be provided with their personalized risk feedback based on a summary of their personalized UV photo and a summary of their MC1R genetic testing results. All information will be delivered at this visit on a computer screen and additionally given to participants as a handout they can take home to review. When participants view their results on the computer screen, eye tracking will be used to assess participant response. Prior to viewing results, eye tracking equipment set up at the computer station will be calibrated. We will then put up their results on the screen and the imotion system will then track their

pupillary movement, facial expression, and galvanic skin response (physiological arousal). Participants will be allowed as much time as they would like to review their results. Following this, participants will complete a post assessment. The imagery resulting will be kept on file in a password protected computer. Participants will receive paper copies of all of the relevant information to take home with them.

Visit 3: Visit 3 may be conducted remotely. At visit 3, participants will complete a follow-up assessment. Participants who have clinical questions about melanoma or concerns about their family history will be referred to speak with a genetic counselor or be referred to HCI's Family Cancer Assessment Clinic (FCAC) for further information and information on CLIA testing.

Follow-up interview: A random sample of the participant population will be contacted to participate in a follow-up interview with study staff to answer questions about their experience participating in the RISE-UP study.

Procedures performed for research purposes only:

Statistical Methods, Data Analysis and Interpretation

Descriptive statistics (number, percent for categorical variables and mean, standard deviation for quantitative variables) were calculated for demographic characteristics and participant's sun protection and tanning outcomes. For inferential statistical analyses, missing data was handled via multiple imputation, which ensures valid inference under missingness-at-random (data values independent of missingness pattern, conditional on the observed data), the most general data-centered missing data assumption. Twenty complete data sets were generated and all statistical analyses were based on these, with pooling via Rubin's rules. The primary outcomes of interest include sun protection and tanning. In order to estimate changes in outcomes over time overall and compare changes over time between the four intervention groups, generalized estimating equations (GEE) were used to account for repeated measures within individuals. Season of participation (fall versus spring) was considered an important factor for the primary outcomes, so it was included as an adjustment factor in all models and outcomes were also examined within each season separately.

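### No stratification or blocking by season is described, and a season main effect cannot remove chance season imbalance from the pooled comparison of change

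*Combined protocol and SAP*

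**What the plan says.** On allocation, the Design section reads "Randomized Trial". Under Study Procedures, the visit 1 paragraph of each of the four arms repeats one sentence: "Participants will be randomized to receive education only, or varying combinations of the intervention components". Sequence generation, allocation ratio, blocking and stratification are not mentioned. The sample size is given as "All Centers: 300".

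On analysis, the section on statistical methods sets out to "compare changes over time between the four intervention groups", and says that "generalized estimating equations (GEE) were used to account for repeated measures within individuals". It adds that "Season of participation (fall versus spring) was considered an important factor for the primary outcomes", and so "it was included as an adjustment factor in all models and outcomes were also examined within each season separately". The model terms and the link function are not written out, and no season-by-visit term is mentioned. Missing values are multiply imputed, so each of the 20 analysed data sets is complete.

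**The concern.** Season has two levels, is known at enrolment, is declared important for the primary outcomes and is used to split the results. That makes it an obvious factor to balance, yet the allocation text does not mention it. A reader may assume that adjusting all models for season makes good any chance imbalance.

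For a comparison of change, that assumption fails. Follow-up spans roughly 8 weeks (up to three visits, about 4 weeks apart), and outdoor exposure can drift differently over those weeks in fall and in spring. If it does, an arm that happens to hold more fall participants shows a different mean change with no intervention effect at all. A season term that is the same at every visit cancels out of change and leaves that difference in place. What is at stake is precision in the main randomised contrast, with 300 people spread over four arms.

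**Working it through.** The plan states no power, SD, effect size or allocation ratio, so it has no figure of its own to reproduce. The check is of the mechanism and its size.

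**Inputs.** From the documents: 300 participants, four arms, a two-level season factor. Assumed: equal allocation (300/4 = 75 per arm), an even season split, identity link, and within-season SD of change equal to 1. D is the fall–spring difference in mean change in SD units. The documents give no value for D, so a range is shown.

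**1. What a season main effect does.** Let person i in arm a have mean μ(a,t) + γ·s(i) at visit t, where s(i) is the season indicator. With complete data, the arm-by-visit cells saturated and an identity link, the estimating equations give μ̂(a,t) = Ȳ(a,t) − γ̂·s̄(a), where s̄(a) is the season share of arm a. The subtracted amount is the same at every visit, so μ̂(a,t) − μ̂(a,0) = Ȳ(a,t) − Ȳ(a,0): the raw mean change, whatever γ̂ is. This holds in each imputed data set and therefore in the pooled result.

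A fitted example (4 × 75 people, 3 visits, exchangeable correlation) agrees:
- arm-by-visit terms only: −0.068 (SE 0.166)
- plus season main effect: −0.068 (SE 0.166)
- plus season-by-visit: −0.167 (SE 0.161)

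**2. Chance imbalance under simple randomisation.** The SD of the difference in season share between two arms is √(2 × 0.5 × 0.5/75) = 0.082, a 95% range of about ±16 points. In simulation, some pair of the four arms differs by at least 10 points in 61% of trials.

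**3. Shift in one contrast for a given imbalance.** Shift = D × difference in season share. For 47 v 32 of 75 (0.20) and D = 0.5, the expected shift is 0.10. Simulated mean estimates, true value 0, Monte Carlo SE 0.009: 0.089 with the main effect and −0.012 with season-by-visit.

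**4. Effect on variance over all randomisations.** With season removed from change, the contrast variance is 2/75 = 0.0267. With it left in, it is (2/75)(1 + 0.25·D²).

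| D (SD) | Variance ratio 1 + 0.25·D² | Effective size of 300 |
|---|---|---|
| 0 | 1.00 | 300 |
| 0.2 | 1.01 | 297 |
| 0.5 | 1.06 | 282 |
| 0.8 | 1.16 | 259 |
| 1.0 | 1.25 | 240 |

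(Effective size = 300 / ratio.) A simulation of simple randomisation at D = 1 gives 0.0335 without and 0.0270 with the season-by-visit term, a ratio of 1.24. For an illustrative arm effect of 0.5 SD, power is 86.5% with season removed, 84.4% with it left in at D = 0.5, and 81.1% at D = 0.8.

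**5. Validity.** Under simple randomisation without season-by-visit, the mean estimate is about 0 and type I error is 4.97% (D = 0.5) and 5.05% (D = 0.8).

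**6. Blocking without the term.** With blocks of 8 within season, D = 1 and season only as a main effect, the true contrast variance is about 0.0270 but the model reports about 0.0335. Intervals are then too wide and type I error falls to about 0.03.

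**The case against.** The strongest case against runs as follows.

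- *Silence is not absence.* A reader might infer that randomisation was not stratified. The documents do not say so: they leave the method unstated, so stratification is neither described nor excluded. This stands. The imbalance figures above apply if allocation was simple.
- *Season is calendar time, so ordinary blocking nearly balances it.* This stands too. With unstratified blocks of 8 in enrolment order (one fall, then one spring), the mean gap in season share between two arms is about 1.1 points, against about 6.5 under simple randomisation. A reader might therefore blame the lack of stratification as such; the documents do not support that. The matters to settle are the unstated sequence method and the missing model term.
- *The within-season analyses already handle it.* They do remove season imbalance from each season's own arm comparison. They do not repair the pooled model, and without blocking their arm sizes are left to chance.
- *The model is not written out.* A main effect is the natural reading of an adjustment factor, not a stated one. With a non-identity link, a main effect could move the estimates slightly. The exact result in step 1 is limited to the linear case.
- *Feasibility is the first stated purpose,* with behavioural effects examined in addition. This supports a low severity. It does not remove the point, because the primary outcomes are behavioural.

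**Conclusion.** The point holds as a modest, inexpensive gain in precision. As the analysis is most naturally read, season adjustment does nothing for the pooled comparison of change in a linear GEE on imputed data. If allocation was simple, pairwise contrasts carry about 6% extra variance at a seasonal difference in change of 0.5 SD and about 25% at 1 SD; with no such difference there is no loss. These differences are assumptions, as are equal arms and an even season split.

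A reader might infer that the arm comparison is biased or its tests invalid. The documents do not support that: the estimate is unbiased over randomisations and type I error stays near 5%. Severity: minor.

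**What to change.** In the statistical methods section, write out the pooled GEE and replace the season main effect with season plus season-by-visit. Report the number in each arm by season, and state how the allocation sequence was generated. The cost is one extra parameter per follow-up visit, using data already collected. Because that section is written in the past tense, this may be the only part still open to change.

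If allocation is still open, also state in the visit 1 text that participants are randomised 1:1:1:1 in permuted blocks of varying size, with a separate list for each term. This takes a new list and one sentence, with no added participants or visits. Late allocations within a block become somewhat easier to guess; varying block sizes and a concealed list limit that. Blocking should always go together with the season-by-visit term, for the reason shown in step 6.

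### The primary behavioural comparison names no visit, although only visit 3 can show a response to the feedback; make it the arm effect at visit 3, adjusted for baseline

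*Combined protocol and SAP*

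**What the plan says.** The timing is in Study Procedures and is the same in all four arms.

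- Visit 1: "At visit 1, all participants will be asked to complete informed consent procedures and a baseline questionnaire via computer". The UV photo (Arms 2 and 4) and the saliva sample (Arms 3 and 4) are also taken here, but no results are given.
- Visit 2, education: "All education will be delivered at this visit on a computer screen and additionally given to participants as a handout".
- Visit 2, feedback, taking Arm 2 as the example: "Participants will be provided with their personalized risk feedback based on their personalized photo showing their skin's existing UVR damage from UVR exposure".
- Visit 2, questionnaire, once the material has been viewed: "Following this, participants will complete a post assessment".
- Visit 3: "At visit 3, participants will complete a follow-up assessment".
- Spacing: "up to 3 study visits approximately 4 weeks apart".

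Statistical Methods, Data Analysis and Interpretation states: "The primary outcomes of interest include sun protection and tanning". Its comparison of arms is worded as "compare changes over time between the four intervention groups, generalized estimating equations (GEE) were used", with season as an adjustment factor. It does not give the assessments used, the coding of time, the working correlation or the primary contrast. The content of the visit 2 questionnaire is not described anywhere.

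**The concern.** The outcomes are self-reported behaviours. A report given minutes after someone first sees the feedback describes behaviour from before the feedback, so it cannot show a behavioural response to it. Yet that questionnaire sits second in a series of three and is labelled as a post measure. An analyst told only to compare change over time could reasonably fit a pre/post indicator, a linear trend or categorical time. These models target different quantities, and one of them would average a visit that cannot carry the effect with the visit that can.

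The size of the primary estimate would then depend on a choice that the plan leaves open. A comparison of changes also uses the baseline questionnaire less efficiently than adjusting for it, and that costs power in any pairwise comparison of arms.

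**Working it through.** **No figure to reproduce.** The plan gives 300 participants with no effect size, SD, power, alpha, allocation ratio or dropout rate. Every power figure below rests on assumptions.

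**Inputs**
- From the documents: 300 participants, four arms, three assessments.
- Assumed: equal allocation (300/4 = 75 per arm), a continuous outcome with SD 1, equal correlation r between visits, complete data, two-sided 5%, and an effect of 0.40 SD at visit 3 and none at visit 2.

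**Step 1. What each coding of time estimates.** In a linear (identity-link) GEE, the between-arm difference in change is a weighted sum of the visit-specific arm differences.

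| Coding of time | Weights on visits 1, 2, 3 | Share of visit 3 effect |
|---|---|---|
| Categorical, visit 3 minus visit 1 | -1, 0, 1 | 100% |
| Linear trend, equal spacing, complete data | -1, 0, 1 | 100% |
| Visits 2 and 3 pooled as post (independence or exchangeable) | -1, 0.5, 0.5 | 50% |

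With an AR(1) working correlation matching the true structure, the pooled coding keeps 35%, 25% and 15% at correlations of 0.3, 0.5 and 0.7. If visit 2 reports carried a share f of the visit 3 effect, equal-weight pooling would keep (1 + f)/2, which is 75% at f = 0.5.

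**Step 2. Pairwise power.** SE = sqrt(2v/75) and power = Φ(estimate/SE - 1.96). The per-person variance v is:
- pooled post minus baseline: 1.5(1 - r)
- visit 3 minus baseline: 2(1 - r)
- visit 3 adjusted for baseline: 1 - r²

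| Contrast | r | Estimate | v | SE | Estimate/SE | Power |
|---|---|---|---|---|---|---|
| Pooled post minus baseline | 0.5 | 0.20 | 0.75 | 0.1414 | 1.414 | 29.3% |
| Visit 3 minus baseline | 0.5 | 0.40 | 1.00 | 0.1633 | 2.449 | 68.8% |
| Visit 3 adjusted for baseline | 0.5 | 0.40 | 0.75 | 0.1414 | 2.828 | 80.7% |
| Pooled post minus baseline | 0.7 | 0.20 | 0.45 | 0.1095 | 1.826 | 44.7% |
| Visit 3 minus baseline | 0.7 | 0.40 | 0.60 | 0.1265 | 3.162 | 88.5% |
| Visit 3 adjusted for baseline | 0.7 | 0.40 | 0.51 | 0.1166 | 3.430 | 92.9% |

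The gain from adjustment does not depend on what visit 2 measures. The variance ratio is (1 - r²)/(2(1 - r)) = (1 + r)/2, which is 0.75 at r = 0.5 and 0.85 at r = 0.7.

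**Step 3. Should visit 2 behaviour be a covariate?** With equal correlations, adjusting for baseline and visit 2 gives each a weight of r/(1 + r). If visit 2 reports carry a share f of the effect, adjustment removes f·r/(1 + r) of it. At an assumed f = 0.5 this is 0.5 × 0.5/1.5 = 17% at r = 0.5, and 0.5 × 0.7/1.7 = 21% at r = 0.7. A non-zero f is plausible. Arms 2 to 4 undergo arm-specific procedures at visit 1, and the visit 2 report is given after arm-specific feedback.

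**The case against.** The strongest objection is that the plan commits no such error. No section says that the visit 2 questionnaire asks about behaviour, that it enters the GEE, or that visits 2 and 3 are merged. The protocol uses different names for the visit 2 and visit 3 questionnaires, and its background section discusses distress about genetic feedback, so visit 2 may cover reactions only. This stands. A reader might infer from the label and position of the visit 2 questionnaire that it is counted as a behavioural follow-up and dilutes the effect. The documents do not support that.

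Dilution also depends on the coding. Step 1 shows none with categorical time and a visit 3 contrast, or with a linear trend on equally spaced complete data. Nor does including visit 2 necessarily cost power in a joint test. With one arm differing by 0.5 SD at visit 3 and r = 0.5, the joint arm-by-time test has power 0.923 with visit 2 (6 df) and 0.898 without it (3 df). This stands too.

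A reader might also infer that visit 2 behaviour cannot differ by arm and so serves as a second baseline. That does not hold, for the reasons in Step 3.

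Finally, preferring baseline adjustment to change scores is a matter of efficiency and is separate from the timing. True, but it uses data already collected, and the same sentence of the plan settles both.

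**Conclusion.** The point holds as a gap in specification with a worthwhile improvement attached. It is not a demonstrated bias. The visit sequence makes visit 3 the only assessment able to show behaviour change due to the feedback, and the analysis section does not tie the primary comparison to it.

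The halving is conditional: it needs behaviour items at visit 2 and pooling with visit 3, and neither is documented. The gain from a baseline-adjusted visit 3 comparison over visit 3 minus baseline needs neither condition. It is about 12 percentage points of pairwise power at r = 0.5 (80.7 - 68.8 = 11.9) and about 4 at r = 0.7 (92.9 - 88.5 = 4.4).

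These figures rest on the assumptions listed under the inputs. A logit or log link, dropout handled by imputation, or unequal spacing would change the numbers but not the pattern.

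**What to change.** In Statistical Methods, Data Analysis and Interpretation:

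1. Make the primary behavioural comparison the arm effect at visit 3 for each primary behaviour, adjusted for the baseline value of that behaviour and for season as already planned.
2. State what each of the three questionnaires measures and the recall period of the behaviour items.
3. Say that any behaviour reported at visit 2 is not pooled with visit 3 and is not a covariate in the primary model, because it is collected after randomisation and after feedback. Use visit 2 for immediate reactions only.
4. If GEE is kept for overall change over time, list the assessments included and treat time as categorical.

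The cost is wording plus a refit of the model, with no new data. The section is written in the past tense. If the analysis has already been run, the re-specified contrast should be labelled as such and reported beside the one originally fitted.
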